7.8 Study collection of adverse events

All adverse events must be reported by study investigators. The Academic Research Organization will collect the source document of all adverse events. The adverse events will be adjudicated by the Clinical Event Committee (CEC). As reported below, the CEC will transfer to DSMB the adverse events.

7.9 Adjudication of clinical events

A committee consisting of clinicians who are blinded to treatment allocation will adjudicate all adverse events. The functioning rules and the membership of the Adjudication Committee are detailed in the Adjudication Committee Charter before the start of the trial. Adjudication results will be binding for the final analysis.

7.10 Role of the Data Safety Monitoring Board (DSMB)

The DSMB is responsible for the following items:

- Analysis of the rate of adverse events in the study arms

- Monitoring of study conduction and of the distribution of adverse events between study arms

The DSMB is responsible for immediately stopping the trial if the rate of adverse events would be higher than expected. DSMB will strictly monitor the rate of adverse events in study arms and will communicate to study leadership if the rate of adverse events is higher than expected in one of the study arms. Anyway, the DSMB:

- will generate a report each 4 months illustrating the trend of adverse events (in line with or not with the expectations)
- will communicate each 4 months to the Steering Committee if the study can continue or not.

8 STUDY DEFINITIONS

8.1 Myocardial Infarction (MI)

MI will be defined according to the 4th universal definition of myocardial infarction²².

Universal definitions of myocardial injury and myocardial infarction
Criteria for myocardial injury
The term myocardial injury should be used when there is evidence of elevated cardiac troponin values (cTn) with at least one value above the 99th percentile upper reference limit (URL). The myocardial injury is considered acute if there is a rise and/or fall of cTn values.
Criteria for acute myocardial infarction (types 1, 2 and 3 MI)
The term acute myocardial infarction should be used when there is acute myocardial injury with clinical evidence of acute myocardial ischaemia and with detection of a rise and/or fall of cTn values with at least one value above the 99th percentile URL and at least one of the following: 
 • Symptoms of myocardial ischaemia; • New ischaemic ECG changes; • Development of pathological Q waves; • Imaging evidence of new loss of viable myocardium or new regional wall motion abnormality in a pattern consistent with an ischaemic aetiology; • Identification of a coronary thrombus by angiography or autopsy (not for types 2 or 3 MIs). Post-mortem demonstration of acute athero-thrombosis in the artery supplying the infarcted myocardium meets criteria for type 1 MI . Evidence of an imbalance between myocardial oxygen supply and demand unrelated to acute athero-thrombosis meets criteria for type 2 MI . Cardiac death in patients with symptoms suggestive of myocardial ischaemia and presumed new ischaemic ECG changes before cTn values become available or abnormal meets criteria for type 3 MI .
Criteria for coronary procedure-related myocardial infarction (types 4 and 5 MI)
Percutaneous coronary intervention (PCI) related MI is termed type 4a MI . Coronary artery bypass grafting (CABG) related MI is termed type 5 MI . Coronary procedure-related MI \leq 48 hours after the index procedure is arbitrarily defined by an elevation of cTn values $>$ 5 times for type 4a MI and $>$ 10 times for type 5 MI of the 99th percentile URL in patients with normal baseline values. Patients with elevated pre-procedural cTn values, in whom the pre-procedural cTn level are stable (\leq 20% variation) or falling, must meet the criteria for a $>$ 5 or $>$ 10 fold increase and manifest a change from the baseline value of $>$ 20%. In addition with at least one of the following: 
 • New ischaemic ECG changes (this criterion is related to type 4a MI only); • Development of new pathological Q waves; • Imaging evidence of loss of viable myocardium that is presumed to be new and in a pattern consistent with an ischaemic aetiology; • Angiographic findings consistent with a procedural flow-limiting complication such as coronary dissection, occlusion of a major epicardial artery or graft, side-branch occlusion-thrombus, disruption of collateral flow or distal embolization. Isolated development of new pathological Q waves meets the type 4a MI or type 5 MI criteria with either revascularization procedure if cTn values are elevated and rising but less than the pre-specified thresholds for PCI and CABG. Other types of 4 MI include type 4b MI stent thrombosis and type 4c MI restenosis that both meet type 1 MI criteria. Post-mortem demonstration of a procedure-related thrombus meets the type 4a MI criteria or type 4b MI criteria if associated with a stent.
Criteria for prior or silent/unrecognized myocardial infarction
Any one of the following criteria meets the diagnosis for prior or silent/unrecognized MI: 
 • Abnormal Q waves with or without symptoms in the absence of non-ischaemic causes. • Imaging evidence of loss of viable myocardium in a pattern consistent with ischaemic aetiology. • Patho-anatomical findings of a prior MI.

©ESC/ACC/AHA/WHF 2018

The leading symptom that initiates the diagnostic and therapeutic cascade in patients with suspected MI is chest pain. Based on the electrocardiogram (ECG), two groups of patients should be differentiated: (1) Patients with acute chest pain and persistent ($>$ 20 min) ST-segment elevation. This condition is termed ST-elevation ACS and generally reflects an acute total coronary occlusion. Most patients will ultimately develop an ST-elevation myocardial infarction (STEMI). The mainstay of treatment in these patients is immediate reperfusion by primary angioplasty or fibrinolytic therapy. (2) Patients with acute chest pain but no persistent ST-segment elevation. ECG changes may include transient ST-segment elevation, persistent or transient ST-segment depression, T-wave inversion, flat T waves or pseudo-normalization of T waves or the

[figure not shown]
ECG may be normal. The clinical spectrum of NSTEMI may range from patients free of symptoms at presentation to individuals with ongoing ischemia, electrical or hemodynamic instability or cardiac arrest. The pathological correlate at the myocardial level is cardiomyocyte necrosis. A small proportion of patients may present with ongoing myocardial ischemia, characterized by one or more of the following: recurrent or ongoing chest pain, marked ST depression on 12-lead ECG, heart failure and hemodynamic or electrical instability. Due to the amount of myocardium in jeopardy and the risk of malignant ventricular arrhythmias, immediate coronary angiography and, if appropriate, revascularization are indicated.

8.1.1 Clinical criteria for MI

The clinical definition of MI denotes the presence of acute myocardial injury detected by abnormal cardiac biomarkers in the setting of evidence of acute myocardial ischaemia.

8.1.2 Criteria for myocardial injury

[figure not shown]
Detection of an elevated cTn value above the 99th percentile URL is defined as myocardial injury. The injury is considered acute if there is a rise and/or fall of cTn values.

Criteria for type 1 MI

Detection of a rise and/or fall of cTn values with at least one value above the 99th percentile URL and with at least one of the following:

[figure not shown]
- Symptoms of acute myocardial ischaemia;
- New ischaemic ECG changes;
- Development of pathological Q waves;
- Imaging evidence of new loss of viable myocardium or new regional wall motion abnormality in a pattern consistent with an ischaemic aetiology;
- Identification of a coronary thrombus by angiography including intracoronary imaging or by autopsy.^a

Criteria for type 2 MI

Detection of a rise and/or fall of cTn values with at least one value above the 99th percentile URL, and evidence of an imbalance between myocardial oxygen supply and demand unrelated to coronary thrombosis, requiring at least one of the following:

- Symptoms of acute myocardial ischaemia;
- New ischaemic ECG changes;
- Development of pathological Q waves;
- Imaging evidence of new loss of viable myocardium or new regional wall motion abnormality in a pattern consistent with an ischaemic aetiology.

Criteria for type 3 MI

Patients who suffer cardiac death, with symptoms suggestive of myocardial ischaemia accompanied by presumed new ischaemic ECG changes or ventricular fibrillation, but die before blood samples for biomarkers can be obtained, or before increases in cardiac biomarkers can be identified, or MI is detected by autopsy examination.

8.1.3 Criteria for spontaneous MI

Spontaneous MI is defined by the presence of acute myocardial injury with clinical evidence of acute myocardial ischemia, with detection of a typical rise and/or fall of cTn values with at least 1 value above the 99th percentile upper reference limit (URL) and at least 1 of the ancillary criteria: symptoms of myocardial ischemia, ischemic ECG changes, pathological Q waves, imaging evidence (e.g., echocardiography), or confirmation of intracoronary thrombus by angiography(including intracoronary imaging) or autopsy^{22,23}.

8.1.4 Criteria for periprocedural MI

We endorse Fourth Universal MI definition criteria for MI related to PCI complications²².

Criteria for PCI-related MI ≤ 48 h after the index procedure (type 4a MI)

Coronary intervention-related MI is arbitrarily defined by an elevation of cTn values more than five times the 99th percentile URL in patients with normal baseline values. In patients with elevated pre-procedure cTn in whom the cTn level are stable ($\leq 20\%$ variation) or falling, the post-procedure cTn must rise by $>20\%$. However, the absolute post-procedural value must still be at least five times the 99th percentile URL. In addition, one of the following elements is required:

- New ischaemic ECG changes;
- Development of new pathological Q waves;^a
- Imaging evidence of new loss of viable myocardium or new regional wall motion abnormality in a pattern consistent with an ischaemic aetiology;
- Angiographic findings consistent with a procedural flow-limiting complication such as coronary dissection, occlusion of a major epicardial artery or a side branch occlusion/thrombus, disruption of collateral flow, or distal embolization.^b

^aIsolated development of new pathological Q waves meets the type 4a MI criteria if cTn values are elevated and rising but more than five times the 99th percentile URL.

^bPost-mortem demonstration of a procedure-related thrombus in the culprit artery, or a macroscopically large circumscribed area of necrosis with or without intra-myocardial haemorrhage meets the type 4a MI criteria.

8.2 Death

Deaths will be classified as cardiovascular, non-cardiovascular or undetermined cause according to ARC-2 criteria²⁴. Deaths of undetermined cause will default to cardiovascular (but will also be reported as a separate subcategory of cardiovascular death to denote this uncertainty). Deaths related to the procedure or complications of the procedure (or concomitant treatment) will be classified as cardiovascular. Within cardiovascular deaths, hemorrhagic deaths will be clearly identified. Only deaths due to a documented non-cardiovascular cause (e.g., cancer) will be classified as non-cardiovascular.

ARC-2 classification of death:

Type of Death	Definition
Cardiovascular death	Cardiovascular death is defined as death resulting from cardiovascular causes. The following categories may be collected: 
 1. Death caused by acute MI 2. Death caused by sudden cardiac, including unwitnessed, death 3. Death resulting from heart failure 4. Death caused by stroke 5. Death caused by cardiovascular procedures 6. Death resulting from cardiovascular hemorrhage 7. Death resulting from other cardiovascular cause
Noncardiovascular death	Noncardiovascular death is defined as any death that is not thought to be the result of a cardiovascular cause. The following categories may be collected: 
 1. Death resulting from malignancy 2. Death resulting from pulmonary causes 3. Death caused by infection (includes sepsis) 4. Death resulting from gastrointestinal causes 5. Death resulting from accident/trauma 6. Death caused by other noncardiovascular organ failure 7. Death resulting from other noncardiovascular cause
Undetermined	Undetermined cause of death is defined as a death not attributable to any other category because of the absence of any relevant source documents. Such deaths will be classified as cardiovascular for end point determination.

MI indicates myocardial infarction.

8.3 Ischemia-driven revascularization

Requires the following criteria:

1. Ischemic symptoms consistent with CCS class ≥ 3 angina despite optimal medical therapy

AND

2. PCI or CABG of either the culprit or a non-culprit lesion that lead to enrollment into the trial PLUS at least ONE of the following:

A. Positive functional study (Exercise or myocardial perfusion imaging or stress or dobutamine echo)

demonstrating clear evidence of reversible ischemia corresponding to a stenosis in a vessel other than the culprit vessel that lead to enrollment into the trial,

OR

B. New ischemic ECG changes (ST-segment depression ≥ 1 mm, ST-segment elevation ≥ 1 mm or T wave

inversion ≥ 2 mm) at rest or with exertion in a distribution consistent with a stenosis in a vessel other than the culprit vessel that lead to enrollment into the trial,

OR

C. $FFR \leq 0.80$, $iFR \leq 0.89$, $cFFR \leq 0.85$, Angiography-derived $FFR \leq 0.80$ in a lesion in a vessel other than the culprit vessel that lead to enrollment into the trial.

All ischemia-driven revascularizations will be sub-categorized as to whether they were due to the culprit lesion or due to a non-culprit lesion that led to enrollment into the trial.

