4 STUDY ENDPOINTS

4.1 Primary efficacy endpoint

- Cumulative occurrence of all-cause mortality, cerebrovascular accident, reinfarction, or ischemia-driven revascularization

To test if a complete revascularization based on functional coronary angiography to indicate and guide PCI is superior to an angio-based strategy in the reduction of all-cause mortality, cerebrovascular accident, reinfarction, or ischemia-driven revascularization

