6 STUDY POPULATION

6.1 Inclusion criteria

1. STEMI with indication to invasive management **AND**
2. Multi-vessel disease defined as at least 1 non-culprit coronary artery lesion at least 2.5 mm in diameter deemed at visual estimation with a diameter stenosis % ranging from 50 to 99% amenable to successful treatment with PCI **AND**
3. Successful treatment of culprit lesion

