7.2 Conventional angiography guided complete revascularization

[figure not shown]
[figure not shown]
All patients randomized to angio-guided revascularization must undergo PCI of all non-culprit lesions angiographically deemed $\geq 50\%$. Complete revascularization must be obtained within index hospitalization.

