7.3 Functional coronary angiography complete revascularization

Patients who are randomized to this strategy will receive revascularization of the culprit lesion and functional coronary angiography evaluation on all non-culprit lesions (angiographically deemed $\geq 50\%$) and revascularization of all-functional positive lesions according to angio-FFR based virtual PCI plan. Functional evaluation is mandatory for all stenosis. When angiography-derived FFR is not feasible with any of the available tools, then a staged procedure to perform invasive FFR is mandatory. According to available literature, the overall rate of invasive FFR should not exceed 5% of the patients. PCI of vessel with negative functional evaluation is considered a protocol violation. Revascularization of the positive (at angiography-derived FFR assessment) non-culprit lesions must be performed within the index hospitalization.

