7.3.1.2 Angiography-derived measurement of plaque vulnerability

In patients randomized to the AIR strategy with negative FFR, a further stratification of NCLs will be performed. Vessels with an angiography-derived measurement of plaque vulnerability above the validate thresholds (RWSmax >12% or TSVI $\geq 40.5 \text{ m}^{-1}$) will receive PCI whereas those below the threshold will be treated with optimal medical therapy (OMT).

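### Section 8.3 counts culprit revascularization in the primary endpoint but accepts ischemia evidence only from outside the culprit vessel; its lesion wording can also miss treated lesions under 2.5 mm

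*Protocol*

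**What the plan says.** Protocol section 4.1 defines the primary efficacy endpoint as "Cumulative occurrence of all-cause mortality, cerebrovascular accident, reinfarction, or ischemia-driven revascularization".

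Section 8.3 defines the last component by conditions that must all hold:

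- **Criterion 1:** angina of CCS class 3 or worse despite optimal medical therapy.
- **Criterion 2:** "PCI or CABG of either the culprit or a non-culprit lesion that lead to enrollment into the trial".
- **At least one of A, B or C**, joined to criterion 2 by PLUS: a positive functional study (A), new ischemic ECG changes (B), or a pressure-based or angiography-derived index at or below its cut-off (C).

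C must be found "in a lesion in a vessel other than the culprit vessel that lead to enrollment into the trial". A and B carry the same restriction in parallel wording. The closing sentence sorts every counted event into one of two classes: "due to the culprit lesion or due to a non-culprit lesion that led to enrollment into the trial".

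On the lesions themselves, section 6.1 requires "at least 1 non-culprit coronary artery lesion at least 2.5 mm in diameter deemed at visual estimation", with 50–99% stenosis and amenable to PCI. Section 7.2 says that ANGIO patients "must undergo PCI of all non-culprit lesions angiographically deemed" 50% or more. Section 7.3 requires functional evaluation of the same lesions in AIR. Neither treatment section repeats a diameter limit.

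**The concern.** Criterion 2 and the closing sentence show that culprit revascularization is meant to be in the endpoint. A–C then exclude the only evidence that would normally support such an event. A committee that follows the text has to reject a well-documented culprit failure. A committee that follows the apparent intent has to depart from the text. Section 5.5 relies on blinded adjudication against pre-determined definitions as a main safeguard in an open-label trial, and section 7.9 makes the adjudicated result binding. A definition that contradicts itself weakens that safeguard.

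The component matters to the hypothesis. Section 2.6 attributes the benefit in the trial that supplies the 35% effect size to fewer infarctions and fewer ischemia-driven revascularizations. Section 4.2 also uses the component alone as a secondary endpoint and within a composite planned for the merged analysis, so the same fault carries into those.

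The second question is whether the lesions counted match the lesions on which the two strategies differ.

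**Working it through.** No arithmetic applies: the protocol gives no figure on this point. The check is to run typical events through 8.3 as written. In each case criterion 1 is taken as met.

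| Event | Criterion 2 | A–C | Counted as written? |
|---|---|---|---|
| 1. Repeat PCI of the culprit stent, FFR of 0.80 or less in the culprit vessel, no evidence elsewhere | Met (culprit) | Not met | No |
| 2. PCI of a non-culprit lesion lying in the culprit vessel and meeting 6.1, FFR of 0.80 or less there | Met | Not met | No |
| 3. Repeat PCI of the culprit stent, positive test only in another vessel's territory | Met (culprit) | Met literally | Yes |
| 4. PCI of a 60% baseline lesion in a 3.0 mm non-culprit artery, FFR of 0.80 or less there | Met | Met | Yes |
| 5. PCI of a 60% baseline lesion in a 2.0 mm branch of a non-culprit artery, FFR of 0.80 or less there | Not met if the lesion must satisfy 6.1 | Met | No on that reading |

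**Rows 1 to 3: the inconsistency.** Row 1 is the plain case. Criterion 2 names the culprit and the closing sentence gives it a class of its own, yet no evidence from the culprit territory is accepted. Row 3 shows the reverse: a culprit procedure can pass on ischemia located somewhere else. The result does not depend on whether the phrase about enrollment in A–C attaches to the culprit vessel or to the other vessel, since the evidence lies outside the culprit vessel either way. Row 2 arises because 7.2 and 7.3 speak of all non-culprit lesions, which on their words can include one in the culprit vessel.

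**What still reaches the primary endpoint.** A culprit failure that presents as infarction counts as reinfarction, and deaths and cerebrovascular accidents are unaffected. What is lost is revascularization for severe angina without another primary event. The vessel-oriented secondary endpoint does not recover row 1, because its revascularization term is limited to non-culprit target vessels.

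**Row 5: the lesion set.** Section 6.1 asks for at least one qualifying lesion and 8.3 uses the indefinite article. Every lesion of at least 2.5 mm, 50–99% and amenable to PCI can therefore be said to have led to enrollment. Patients with a chronic total occlusion are excluded (6.2), so the 99% ceiling adds no real gap. A lesion not amenable to PCI could not be stented in ANGIO. What remains is essentially lesions of 50% or more in vessels under 2.5 mm. As 7.2 and 7.3 are worded, ANGIO stents such a lesion. AIR leaves it on medical therapy if it is functionally negative and below the vulnerability thresholds of 7.3.1.2.

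**The case against.** The best counter-argument is that 8.3 is loosely written and will be applied sensibly. The lesion restriction is the same in both arms, adjudication is blinded, and limiting the component to lesions under study is a legitimate choice. Section 6.1 can be read as defining the non-culprit disease that 7.2 and 7.3 then treat; if its 2.5 mm limit carries through, the counted and treated sets nearly coincide. A–C also work at vessel level, which suggests that the enrollment phrase was not meant as a strict lesion filter.

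Most of this stands against the second gap, which is why that gap is secondary and conditional on the reading. It does not answer the first. No reading of A–C admits evidence from the culprit vessel, and no reading of criterion 2 leaves the culprit out.

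A reader might infer three stronger claims that the documents do not support:

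- **Only one index lesion per patient counts.** Nothing designates such a lesion, and the wording of 6.1 and 8.3 points away from it.
- **The definition favors AIR by hiding revascularization of deferred lesions.** ANGIO stents the same lesions, and failures of those stents would go uncounted too. The culprit is treated before randomization in every patient (5.3). The net direction is unknown.
- **The loss can be sized in events or power.** The protocol gives neither the share of patients with a lesion of 50% or more under 2.5 mm nor a rate of culprit revascularization without infarction. The 5-year nontarget-vessel figure in section 2.5 is a patient-level rate in untreated vessels of any stenosis, under a different revascularization rule. Nor does the protocol say whether the 9% control rate was set with this definition; if it was, no power is lost.

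**Conclusion.** Section 8.3 is internally inconsistent on a component of the primary endpoint, and that conclusion needs no assumption beyond reading the text. Followed as written, an ischemia-proven repeat revascularization of the culprit, or of a non-culprit lesion in the culprit vessel, cannot qualify on its own evidence.

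The narrower lesion set holds only conditionally. If a lesion that led to enrollment means one meeting 6.1, and if 7.2 and 7.3 carry no implied diameter limit, then lesions of 50% or more in vessels under 2.5 mm are treated or deferred by strategy but not counted when later revascularized.

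Size and direction cannot be derived from the documents for either point, so none is given. The change should be made because the definition is binding, the fault concerns the primary endpoint and the repair is inexpensive. The finding does not show that the trial is biased or underpowered. That entry requires one qualifying lesion while treatment covers all lesions of 50% or more is ordinary complete revascularization and is not criticized.

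**What to change.** Amend section 8.3 in one edit:

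- **A, B and C:** require the evidence in the vessel or lesion actually revascularized, and remove the restriction to vessels other than the culprit vessel.
- **Criterion 2 and the closing sentence:** refer to *the culprit lesion or any non-culprit lesion of 50% or more on the baseline angiogram*. Membership should be set by baseline anatomy and not by whether the assigned strategy was applied, so that endpoint eligibility does not depend on conduct after randomization.

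Carry the same wording into the adjudication charter. Sections 7.2 and 7.3 need no change.

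The cost is a wording amendment to the protocol and charter, and the committee's work in matching each later revascularization to a baseline lesion. Much of the material is already planned: 5.3 records coronary anatomy in the eCRF, and the core lab reviews stenosis on all angiograms (section 12). Lesions that are new, or below 50% at baseline and later progress, stay outside the definition unless the sponsor decides to include them. Any event already adjudicated under the present text would need a blinded second look.
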